### **9.3 Subject Privacy**

Privacy will be maintained through use of private rooms for the consent process and study procedures. ClinCards will be used for subject compensation and for the intervention — as ClinCards are commonly used for many kinds of research studies, they will not identify participants as recipients of a cash benefit. W9 and C2 forms will be collected for all participants during their enrollment period. These forms will be filled out on paper and stored in a secure location in the research office. W9 forms will be shredded at the end of the study once entered in the Greenphire W-9 database.

### **9.4 Data Disclosure**

Data may be disclosed to The Office of Human Research Protections at the University of Pennsylvania, federal and state agencies (for example, the Department of Health and Human Services, the National Institutes of Health, and /or the Office for Human Research Protections), or other domestic or foreign government bodies if required by law and/ or necessary for oversight purposes.

Otherwise, data will not be disclosed to anyone who is not listed under study personnel.

## **Protected Health Information/ Data Protection**

- **Name**
- Street address, city, county, precinct, **zip code**, and equivalent geocodes
- **Telephone** and fax number
- **Social Security Number**

## **Genetic testing**

N/A

## **CONSENT**

### **Consent Process, Children and Adolescents**

Not applicable. We are only enrolling subjects 18 years of age and older

## **9.5 Data Safety and Monitoring**

Our Study Safety Officer, [name], will be responsible for monitoring the data safety and quality and ensuring that all relevant IRB policies, procedures, and stipulations are followed. These responsibilities will include ensuring that other investigators and project staff adhere to the IRB regulations and policies including processes for: (1) obtaining informed consent; (2) informing participants how to contact the PI, study coordinator, or IRB office with questions and/or concerns; (3) strictly adhering to a participant's right to withdraw from the study or decline to answer questions; (4) maintaining participant confidentiality and data de-identification processes; (5) securely storing data; (6) submitting any amendments to the IRB for approval prior to implementing changes to the protocol; and (7) monitoring and reporting adverse events.

## **9.6 Risk/Benefit**

### **9.6.1 Potential Study Risks**

As this study does not involve changes to standard patient care or medical decision making, we consider this study minimal risk. The primary risk is a breach of confidentiality. This risk has been mitigated by extensive privacy protection protocols, a highly secure data storage system, and a plan to remove identifiers from the data wherever possible. In addition, all personnel will be held to high standards of upholding confidentiality and safeguarding patient privacy.

In addition, for participants receiving the intervention there is the risk that the Social Security Administration (SSA) may decide that participants receiving Supplemental Security Income (SSI) benefits have been slightly overpaid during the four months of the study. SSA may ask them to return the overpayment, but should not (by themselves) affect their eligibility for SSI Benefits. Participants may ask SSA to waive recovery of the overpaid money by going to their local Social Security office. Our team has received correspondence (attached to application) from the state of Pennsylvania confirming that study payments are not considered countable income for the following government programs, and therefore will be no loss to these benefits:

- Temporary Assistance for Needy Families (TANF),
- Modified Adjusted Gross Income (MAGI) Medical Assistance (MA),

- non-MAGI MA including Home and Community-Based Services categories,
- Supplemental Nutrition Assistance Program (SNAP),
- Low-Income Household Water Assistance Program (LIHWAP), and
- Low-Income Home Energy Assistance Program (LIHEAP).

Low-income individuals will address their experiences with poverty and receipt of short-term cash transfers. These can be sensitive topics and may cause some minor distress. These participants will be offered a referral list for social services resources designed to provide financial support.

### **9.6.2 Potential Study Benefits**

The direct benefits of this study for participants in the intervention arm may include improvements in health outcomes. It is possible, however, that the benefits for these participants will be minimal. The control group is unlikely to directly benefit, as this group will continue to simply receive usual care. Participants may benefit indirectly through the knowledge gained in this study, which could assist in the development of interventions to improve health outcomes for people with chronic diseases.

### **9.6.3 Alternatives to Participation**

Patients are free not to participate in this study and non-participation will result in no change in the usual care received from their health care providers.

### **9.6.4 Risk/ Benefit Assessment**

Because this study does not pose more than minimal risk for study participants, we believe the benefits of this study outweigh the risks involved.

## Instructions

The Analysis Plan differs from the AsPredicted in that we expect analysts to update it at important milestones:

1. Beginning analysis X
2. Submitting draft to journal
3. Submitting revision to journal
4. Accepted paper to journal

## **Paper 1: covers Aims 1 and 2 (i.e., everything except qualitative data)**

Aim 1: To determine the effect of an unconditional cash transfer provision on specific health behaviors that influence CVD risk, financial outcomes, and health risk factors that are directly related to insufficient financial resources (food and utility security) (Stage 1, create and test new behavioral interventions) & Aim 2: Assess potential psychological mechanisms through which the intervention influences cardiovascular health (Stage 0, research on mechanisms of change)

## **Dataset**

**Sample:** Survey and measurement data from 100 participants at baseline and 3-month follow-up in a two-arm randomized controlled trial (50 in control, 50 in intervention). Participants are adult patients at UPenn Family Care on Medicaid with either a prediabetes, diabetes, or hypertension diagnosis who have received care there in the past 6 months, live in the greater Philadelphia area, and are actively prescribed oral medication for diabetes or hypertension. Participants will be recruited using UPenn Family Clinic EHRs. Initial interest data will be collected via a REDCap online survey. Most other data will be collected through REDCap surveys completed in-person at the baseline and 3-month visits. Participants' blood pressure and height and weight measurements will also be taken at these visits, and participants will complete a psychomotor vigilance task as well as a behavioral snack choice. 16 participants will receive a blood pressure cuff to take home and send measurements weekly (for 16 weeks; 8 control, 8 intervention; half of each group will transmit wirelessly, the other half won't). These participants will be texted REDCap surveys to fill out weekly with blood pressure measurements. Finally, participant EHR data will be pulled for the 3 months prior to their baseline measurement and 3 months after matched on name and birthdate.

**Intervention:** In the unconditional cash transfer intervention, participants will receive \$125 every 2 weeks for 8 payments via ClinCard, for a total of \$1000.

**Primary Outcome:** Our 8 primary outcomes for this pilot study are:

1. food security (3-category, US Dept of Agriculture) (Aim 1)
2. utility security (5-category; Home Energy Insecurity Scale) (Aim 1)
3. financial well-being scale (0-100, Consumer Financial Protection Bureau Financial Well-Being) (Aim 1)
4. Perceived Stress Scale (0-16, short form) (Aim 2)
5. state anxiety scale from the State Trait Anxiety Inventory (standardized score as per the manual) (Aim 2)
6. number of lapses in the Psychomotor Vigilance Task (Aim 2)
7. health care expenditures on medications (raw dollars) (Aim 1)
8. adherence to medication refills subscale (4-16; Adherence to Refills and Medications Scale (ARMS)) (Aim 1)

Aim 1 = Specific health behaviors

Aim 2 = Potential psychological mechanisms

**Covariates:** To assess the impact of imbalance in baseline covariates, outcomes will be reanalyzed in models that adjust for baseline covariates that differ significantly at the 0.05 level by study arm. These include:

- Sociodemographics: age, sex, gender, low-income vs other-income zipcode, race, ethnicity, sexual orientation, marital status, schooling attainment, being a parent, number of children
- Economic data: work, income sources (including government programs such as SNAP, TANF, and WIC), and total household income
- Housing data: living situation, household composition, and housing security
- Number of chronic medications
- Chronic medical conditions (problem list) – especially the 3 inclusion criteria: prediabetes, diabetes, and hypertension

**Potential Moderators:** In exploratory analyses, to examine whether the intervention impacts health inequities within the sample population, we will assess the intervention effects on physical and mental health across several sociodemographic categories (as tested in Jaroszewicz et al, 2022 RCT with 5,243 participants; \$500 or \$2000 one-time transfers (participant median monthly income = \$1000)).

- Gender (binary: female)
- Race (binary: not exclusively white)\*
- Age (continuous)
- SES
  - Household income level as % FPL (continuous)
  - Yost SES Quintile (binary: lowest vs other; factor analysis of 7 ACS variables; used by SEER; instead of ADI based on Boscoe et al, 2021)
  - Income sources (binary: received governmental assistance at baseline)
  - Work (binary: being employed at baseline)

- Schooling attainment (binary: completed at least high school)
- Family structure
  - Being a parent (binary)
  - Number of children (continuous)
  - Fraction of one's children who are male (proportion)\*
  - Marital status (binary: having a partner or spouse)\*

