Models will include intervention, measurement timepoint, and the interaction of intervention and measurement timepoint as categorical variables. The primary analysis testing the effectiveness of the cash transfers compared to the control arm will be evaluated by the test of the null hypothesis that the intervention-measurement timepoint interaction coefficient is 0, denoting no difference in the change in respective outcomes from baseline to month 3 between intervention and control. We will evaluate the sensitivity of estimated intervention effects to imbalances in baseline covariates and missing data. To assess the impact of imbalance in baseline covariates, outcomes will be reanalyzed in models that adjust for baseline covariates that differ significantly at the 0.05 level by condition. We will evaluate sensitivity to missing data by inverse probability of weighted GEE and multiple imputation. The Holm procedure at a family-wise error rate of 0.05 will be used to account for multiple comparisons in testing differences in 9 primary outcomes between the two groups (number of ED visits, number of non-ED visits, medication adherence, smoking, alcohol use, food security, utility security, health expenditures, and financial stress).

Aim 3 – Qualitative interviews: Qualitative analyses will be guided by an integrated approach that includes identification of a priori attributes of interest and identification of emergent codes and themes. A comprehensive coding scheme will be developed and applied to all data to produce a fine-grained descriptive analysis. All transcribed interview data will be imported into Nvivo for thematic coding. A single analyst will review and code all transcripts. The analysis will yield an understanding of any unanticipated or anticipated consequences of the study and cash transfer provision while also elucidating pathways through which cash transfers influence health behavior.

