## Data Analysis

**Primary Statistical Methods & Software:** All outcomes will be analyzed at the participant level. Analyses will employ population-averaged marginal models estimated by Generalized Estimating Equations (GEE) to account for correlations among the within-person baseline and follow-up measurements. Marginal models estimated by GEE are advantageous for their population-level interpretation and robustness of estimated effects to the assumed correlation structure among repeated measurements (meaning unbiased estimates of the effect of the behavioral intervention will be obtained whether or not the correlation among repeated measurements within a participant is modeled correctly). Clusters will be defined at the level of the participant for all analyses, and independent working correlation will be assumed. Linear models will be used for continuous outcomes and logistic models for categorical or ordinal outcomes. Analyses will be conducted using Stata.

Models will include intervention, measurement timepoint, and the interaction of intervention and measurement timepoint as categorical variables. The primary analysis testing the effectiveness of the cash transfers compared to the control arm will be evaluated by the test of the null hypothesis that the intervention-measurement timepoint interaction coefficient is 0, denoting no difference in the change in respective outcomes from baseline to month 3 between intervention and control. The Holm procedure at a family-wise error rate of 0.05 will be used to account for multiple comparisons in testing differences in the 8 primary outcomes between the two groups.

**Exclusion Criteria & Restrictions:** Physician co-investigators will clarify any values that appear out of range (e.g., biologically implausible values) prior to excluding any data. Any data that are excluded will be done prior to re-matching participants to study arm.

**Assumption Checking & Data Cleaning:** Data will be descriptively summarized and evaluated for quality prior to analyses. Means and standard deviations will be used to characterize continuous variables such as weight and blood pressure, and frequencies and percentages will be used to describe categorical variables. Medians and interquartile ranges will be reported for continuous variables that exhibit skewness. Data will be descriptively summarized overall and by study arm.

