As a manipulation check, we can also download the Clincard data to see how much money is left on people's cards at the end of the study.

**Missing Data:** Although we expect to have minimal missing data because most questionnaire items are required, we will consider other analytic techniques like inverse probability of weighted GEE and multiple imputation to handle missing data (e.g., due to loss to follow-up) if the amount is greater than 10%.

**Secondary Analyses:** *[Could be subgroup analyses, sensitivity analyses, exploratory analyses]*

- If there is enough variation in moderators, exploratory moderation analyses will test how they impact the main effect. Given the pilot nature of this study, we will focus first on household income % of the federal poverty line, but other moderators will be considered.
- Our 10 secondary outcomes include:
  1. number of Emergency Department (ED) visits (from the Electronic Health Record (EHR))
  2. number of non-ED visits (EHR)
  3. smoking (5-25, Cigarette Dependence Scale, short version (CDS-5))
  4. alcohol use (0-12, Alcohol Use Disorders Identification Test (AUDIT-C))
  5. all health care expenditures (raw dollars, medications + office visits + ER visits)
  6. time preference: patience item (0-10)
  7. time preference: behavioral choice task (binary)
  8. Kessler Psychological Distress Scale (6-30, K6+)
  9. self-reported number of healthy days from (CDC health-related quality of life HRQOL-4)
  10. medication taking adherence subscale (ARMS)
- Exploratory health outcomes include objectively measured body mass index and systolic and diastolic blood pressure.
- Secondary analyses of medication adherence will compare the self-reported medication adherence refills (ARMS) to EHR frequency of medication refills (i.e., combining medication name, recommended frequency of use, quantity prescribed, number of refills per prescription, and refill start date) as a proxy for adherence. Note: Refills are requested by pharmacies or patients, so pharmacy refill requests could bias toward adherence.
  - If there is a strong relationship between the ARMS and the EHR prescription measure, we will analyze the EHR prescription measure as a secondary outcome.
- We will assess whether the Acceptability of Intervention Measure (4-item mean, 1-5) varies by any demographic characteristics.

**Table Shells:** *[Not required to include these, but they may help focus the analysis plan, or help get the paper started]*

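### For the six linear primary outcomes in the SAP, the planned baseline-imbalance re-analysis cannot change the treatment estimate, and it picks its covariates by p<0.05

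*SAP*

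**What the plan says.** Protocol section 7 (Analysis Plan) states the aim: "We will evaluate the sensitivity of estimated intervention effects to imbalances in baseline covariates and missing data". The method it gives for imbalance is that "outcomes will be reanalyzed in models that adjust for baseline covariates that differ significantly at the 0.05 level by condition". The Covariates paragraph of the SAP's Dataset section repeats the rule ("outcomes will be reanalyzed in models that adjust for baseline covariates that differ significantly at the 0.05 level by study arm") and lists the candidate covariates.

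The model being re-run is set out under Data Analysis in the SAP. It is a GEE clustered on participant with an independence working correlation: "Models will include intervention, measurement timepoint, and the interaction of intervention and measurement timepoint as categorical variables". The test is on the interaction coefficient, a zero value "denoting no difference in the change in respective outcomes from baseline to month 3 between intervention and control". On model type: "Linear models will be used for continuous outcomes and logistic models for categorical or ordinal outcomes". Neither document mentions a covariate-by-time term, a month-3 model conditional on baseline, or the type of standard error.

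**The concern.** The check exists to show whether chance imbalance moved the treatment estimate. A covariate that does not vary over time, entered as a main effect, shifts both of a participant's visits equally and so drops out of the change. The re-analysis would then reproduce the primary estimate by construction, and the agreement could be reported as robustness.

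The pilot's estimates are meant to supply plausible effect sizes for a larger trial (Protocol section 2), and no other imbalance check is planned. The selection rule is a second weakness. Between randomised arms, p<0.05 identifies chance differences. It says nothing about whether a covariate predicts the outcome, and it leaves the adjusted model unknown until the data are seen.

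**Working it through.** **Inputs from the documents.** There are 50 participants per arm and two visits. The model has arm, time and arm-by-time terms with independence working correlation. Of the SAP's eight primary outcomes, food security (3 categories) and utility security (5 categories) are categorical and so logistic. The other six (items 3 to 8) are treated as linear. That counts vigilance-task lapses and dollars as continuous, because only linear and logistic models are named. The documents give no figure for the effect of imbalance, so there is none to reproduce.

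**1. Why the estimate cannot move.** Let A be arm and t = 0, 1 the visit. After removing the arm and time terms, the interaction column is (A − mean A) × (t − ½). For a covariate X that is constant over visits, the cross-product within one participant is

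X × (A − mean A) × (−½ + ½) = 0.

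The interaction column is therefore orthogonal to X, and adding X leaves the coefficient unchanged. The robust variance uses each participant's difference between the two residuals. X enters both residuals equally and cancels there too.

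**2. Numerical check.** Gaussian GEE, independence, 50 per arm, both visits present, 8 scenarios of 500 datasets each. The largest change on adding the covariate main effect was 6.7e-16 in the estimate and 1.3e-15 in the robust SE, which is rounding error.

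**3. What is left uncorrected.** If X has slope b0 at baseline and b1 at month 3, and the arms differ by d SD on X, the difference in change is off by

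(b1 − b0) × d.

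Illustration, all values assumed: d = 0.39, b1 = 0.5, residual SD 1, residual correlation 0.5, no true effect.

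| b0 | (b1 − b0) × 0.39 | Simulated mean, planned model (same after main-effect adjustment) |
|---|---|---|
| 0.5 | 0 | −0.010 |
| 0.4 | 0.039 | 0.051 |
| 0.25 | 0.098 | 0.095 |
| 0 | 0.195 | 0.199 |

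At d = 0.5, large enough to be selected, the last row becomes 0.5 × 0.5 = 0.25 (simulated 0.255). Main-effect adjustment again changes nothing.

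**4. Models that do respond.** In the d = 0.39 scenarios, covariate-by-time terms bring the mean to between −0.012 and 0.012. A month-3 ANCOVA with the covariate brings it to between −0.008 and 0.006. The ANCOVA SE is 0.177, against 0.197 to 0.221 for the planned GEE.

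**5. Cases where something moves.**
- *Model-based SE, equal slopes:* the SE falls from 0.316 to 0.282 while the estimate stays put, so the p-value shrinks with no correction made.
- *Missing month-3 values at random:* the mean absolute shift is 0.018, 0.023 and 0.039 at 5%, 10% and 20% missing. Among completers it is zero again.
- *Logistic outcomes (binary simplification):* with a covariate acting equally at both visits, the mean absolute shift is 0.045 on the log-odds scale. With one acting only at follow-up, the mean interaction goes from 0.259 to 0.268, which is not towards the true value of 0.

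**6. The p<0.05 screen.** The SAP list has 11 + 3 + 3 + 1 + 1 = 19 items, or 21 if the three diagnoses count separately. Expected chance flags are 19 × 0.05 = 0.95 to 21 × 0.05 = 1.05. For a continuous covariate compared by t-test, the smallest flagged difference is t(98; 0.975) × √(2/50) = 1.984 × 0.2 = 0.397 SD (0.392 with the normal quantile).

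**The case against.** The strongest reply is that the documents say only that models will adjust, which does not exclude covariate-by-time terms. That is true. But neither document mentions such terms, and an analyst following the text would add main effects. If interactions were intended, one sentence settles it.

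Second, the exact result needs both visits, and the SAP provides for methods "to handle missing data (e.g., due to loss to follow-up) if the amount is greater than 10" per cent. The condition is real. However, movement caused by incomplete pairs reflects who is missing, and so does not measure imbalance. The SAP also expects little missing data.

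Third, for covariates acting equally at both visits, no movement is the right answer. This stands: the defect concerns covariates that predict change, and the documents do not show that any listed covariate does so. The check still cannot tell the two situations apart.

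Fourth, d = 0.39 falls just under the selection threshold, and the slopes are assumed. Both points are fair, but the result is the same at d = 0.5, and the invariance does not depend on the slopes.

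Fifth, chance imbalance is not bias over repeated randomisations, and the standard error already allows for it. This is correct, and it limits the point to a sensitivity analysis. The exploratory moderator models might contain covariate-by-time terms, but they ask a different question and are not presented as imbalance checks.

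Finally, several listed covariates are categorical or cover several variables, and no screening test is named. The 0.40 SD threshold and the count of about one chance flag are therefore approximate.

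**Conclusion.** The concern holds. On the ordinary reading, the re-analysis cannot do what Protocol section 7 and the SAP say it is for on six of the eight SAP primary outcomes: the estimate and robust SE are identical with and without the covariates. This rests on main-effect entry, the linear model for items 3 to 8, and both visits observed for everyone analysed. For food and utility security the coefficient does move, but partly through non-collapsibility, so the movement is not clean evidence either.

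The size of any distortion in this trial is unknown; the illustration spans 0 to about 0.2 SD at an imbalance of 0.39 SD. The validity of the randomised primary comparison is not in question. What is affected is the reassurance drawn from the check and the effect sizes carried into the larger trial. The p<0.05 screen is a separate weakness and should be removed whichever model form is chosen.

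**What to change.** In SAP Dataset (Covariates) and Protocol section 7, delete the 0.05 selection rule and write, for example:

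> Adjusted sensitivity analyses will use a fixed list of prognostic baseline covariates [investigators to name a short list, e.g. age, sex, household income, number of chronic medications], whatever their baseline p-values. For linear outcomes each covariate enters with its interaction with timepoint [or: the month-3 value is regressed on arm, the baseline value of the outcome and these covariates]. For food and utility security and other categorical outcomes, a month-3 logistic model (ordinal where applicable) will include arm, the baseline outcome and the same covariates; adjusted odds ratios are not directly comparable with unadjusted ones. All GEE models will use robust, participant-clustered standard errors.

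The covariate-by-time form is the like-for-like comparison with the primary model. If the month-3 form is chosen, report it with and without the covariates, so that their effect is separated from that of conditioning on the baseline outcome.

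The cost is wording in two documents and a few degrees of freedom; no new data are needed. In the illustration the covariate-by-time form gains little precision (SE about 0.20), while the month-3 form does gain some (0.177, under the assumed correlation of 0.5). The list should be fixed before outcomes are examined by arm.
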